4.2.2. Adherence to Study Drug

The total number of doses administered will be summarized using descriptive statistics for each study drug.

The presumed total number of doses administered to a subject will be determined by the data collected on the drug accountability CRF using the following formula:

$$\text{Total Number of Doses Administered} = \left(\sum \text{No. of Doses Dispensed} \right) - \left(\sum \text{No. of Doses Returned} \right)$$

If a bottle was dispensed and returned empty, then the number of tablets returned will be counted as zero. If a bottle was dispensed but not returned (missing), zero tablets from that bottle will be considered to be returned.

If calculated adherence is greater than 100%, the result will be set to 100%.

For each subject, the adherence will be calculated separately for each treatment administered: lanraplenib 30 mg/PTM, filgotinib 200 mg/PTM, or tirabrutinib 40 mg/PTM. The overall adherence to study drug will be defined as the lowest of the three.

4.2.2.1. Prescribed Adherence

The level of prescribed adherence to the study drug regimen will be determined by the total amount of study drug administered relative to the total amount of study drug specified by the protocol for a subject who completes treatment in the study.

The total amount of study drug administered up to week 12/24 will be calculated based on the drug accountability reported on CRF: (total pills dispensed – total pills returned) up to Week 12/24 visit.

The level of prescribed adherence will be expressed as a percentage using the following formula:

$$\text{Prescribed Adherence (\%)} = \left(\frac{\text{Total Amount of Study Drug Administered}}{\text{Total Amount of Study Drug Specified by Protocol}} \right) \times 100$$

Descriptive statistics for the level of prescribed adherence up to Week 12, up to Week 24, and the entire study duration as well as the number and percentage of subjects in each of the two adherence categories, $< 80\%$ and $\geq 80\%$, will be presented by treatment group for the Safety Analysis Set.

The expected amount of study drug to be administered per protocol is defined as follows:

- Up to Week 12: $84 (7 * 12)$ doses
- Up to Week 24: $168 (7 * 24)$ doses
- Entire study duration: $336 (7 * 48)$ doses

No formal statistical testing is planned.

By-subject listings of study drug administration and accountability will be provided separately by subject ID number in ascending order and in chronological order for each treatment separately.

4.3. Protocol Deviations

Subjects who did not meet the eligibility criteria for study entry but enrolled in the study will be summarized. The summary will present the number and percentage of subjects who did not meet at least 1 eligibility criterion and the number of subjects who did not meet specific criteria by treatment group based on the All Randomized Analysis Set. A by-subject listing will be provided for those subjects who did not meet at least 1 eligibility (inclusion or exclusion) criterion. The listing will present the eligibility criterion (or criteria if more than 1 deviation) that subjects did not meet and the related comments, if collected.

Protocol deviations occurring after subjects entered the study are documented during routine monitoring. The number and percentage of subjects with important protocol deviations by deviation reason (e.g., non-adherence to study drug, violation of select inclusion/exclusion criteria) will be summarized by treatment group for the Safety Analysis Set. A by-subject listing will be provided for those subjects with important protocol deviations.

5. BASELINE CHARACTERISTICS

5.1. Demographics

Subject demographic variables will be summarized by treatment group and overall using descriptive statistics for continuous variables, and using number and percentage of subjects for categorical variables. The summary of demographic data will be provided for the Safety Analysis Set for the following:

- age (on the first dose date of any study drug) as a continuous variable
- age group (< 50 years, ≥ 50 years)
- sex at birth (male, female)
- race
- ethnicity (Hispanic or Latino, not Hispanic or Latino)
- geographic region and country

Subject demographic variables (i.e., age, sex, race, and ethnicity) will be summarized by treatment group and overall using descriptive statistics for age, and using number and percentage of subjects for sex, race, and ethnicity.

A by-subject demographic listing, including the informed consent date, will be provided by subject ID number in ascending order.

5.2. Baseline Characteristics

Baseline characteristics include:

- Weight (kg)
- Body mass index (BMI; in kg/m²)
- Concurrent immunomodulatory drugs at baseline (Y/N: conventional synthetic disease modifying antirheumatic drugs (csDMARD[s]) or corticosteroids on Day 1)
- Concurrent background disease-modifying antirheumatic drug [DMARD] use (Yes, No)
- Concurrent use of systemic (oral) corticosteroids at baseline (Yes, No)
- Concurrent background use of anti-malarial DMARDs at baseline (Yes, No)
- hsCRP (descriptive statistics and categories above/below 1.5 ULN)

- ESSDAI (descriptive statistics and categories (<14 and >=14))
- ESSPRI (descriptive statistics)
- Diagnosis of autoimmune disease (Yes and No)
- Diagnosis of SLE (Yes, No)
- Diagnosis of RA (Yes, No)
- Diagnosis of SLE or RA (Yes, No)
- Duration of SjS disease (<5 years, >= 5 years)
- Hematological + biological component scores of the ESSDAI obtained at screening (combined score of <2 or ≥ 2)
- Baseline VAS: patient's global assessment of SjS, pain, fatigue, oral dryness, ocular dryness, vaginal dryness, sexual function, physician's global assessment of SjS
- Baseline Trail Making Test part A (TMT-A) and Trail Making Test part B (TMT-B)
- Baseline Schirmer's test result (average of eyes)
- Baseline unstimulated and stimulated salivary flow rate
- Baseline swollen and tender joint count (descriptive statistic and categorical: n > 0)
- SS-A and SS-B antibodies at baseline (positive and negative)

The time from SjS diagnosis will be calculated in years between the date of enrollment and the date of diagnosis. The missing month will be imputed with January; the missing day will be imputed with 1st day of the month.

These baseline characteristics will be summarized by treatment group and overall using descriptive statistics (n, mean, SD, median, Q1, Q3, minimum, and maximum) for continuous variables, and using number and percentage of subjects for categorical variables. The summary of baseline characteristics will be provided for the FAS. No formal statistical testing is planned.

A by-subject listing of other baseline characteristics will be provided by subject ID number in ascending order.

5.3. Medical History

Medical history will be collected at screening for SjS and other conditions.

The medical history data will be coded using the Medical Dictionary for Regulatory Activities (MedDRA).

Medical history will be summarized by system organ class (SOC), preferred term (PT), treatment group, and overall. Subjects who report 2 or more medical history items that are coded to the same SOC and/or PT will be counted only once by the unique coded term in the summary. The summary will be provided for the Safety Analysis Set. No formal statistical testing is planned.

The autoimmune comorbidities will be identified by Clinical Research based on MedDRA preferred terms.

6. EFFICACY ANALYSES

Efficacy endpoints will be evaluated for the following treatment periods: placebo-controlled period up to Week 24 and the entire study up to Week 48.

The primary and secondary endpoints analyses will be based on the estimands presented in the [Table 3](#).

Table 3. Efficacy Estimands

Binary Endpoint	Treatment Policy (main)	Hypothetical	Composite
Population	FAS	FAS	FAS
Intercurrent Event	Ignore all intercurrent events	
 • Treatment discontinuation • Start of prohibited medication • The dose change of medication that is required to be stable Data after the event are treated as missing	
 • Treatment discontinuation • Start of prohibited medication • The dose change of medication that is required to be stable Data after the event are treated as no response
Main Estimator	Stratified CMH test with imputation of missing data using logistic regression	Stratified CMH test with imputation of missing data using logistic regression	Stratified CMH test with non-responder imputation of missing data

Continuous Endpoints	Treatment Policy (main)	Hypothetical	Composite
Intercurrent Event	Ignore all intercurrent events	
 • Treatment discontinuation • Start of prohibited medication • The dose change of medication that is required to be stable 	
 • Treatment discontinuation • Start of prohibited medication • The dose change of medication that is required to be stable
Main Estimator	The treatment difference will be estimated using a mixed effects model for repeated measures. Missing data will be imputed using multiple imputation	The treatment difference will be estimated using a mixed effects model for repeated measures. Missing data will be imputed using multiple imputation	The treatment difference will be estimated using a mixed effects model for repeated measures. Missing data will be imputed using multiple imputation based on observed data from the placebo group

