6.1. Multiple Imputations of Missing Data

Multiple imputation of binary variables: The MI procedure replaces each missing binary response value with a set of plausible values that represent the uncertainty about the right value to impute. Twenty imputed datasets will be generated based on logistic regression models. These multiple imputed data sets are then analyzed by using the same method for the primary analysis for complete data as specified in Section 6.3. The results from each set of imputed data sets will then be combined using Rubin's rule {Rubin 1987}. Stratification factors will be included in the imputation model.

Multiple imputation of continuous variables: All subjects with baseline measurement will be included. The MI procedure replaces each missing value with a set of plausible values that represent the uncertainty about the right value to impute. Twenty imputed datasets will be generated based on linear regression models on observed values. These multiple imputed data sets are then analyzed by using the analysis method specified in Section 6.4 for complete data. The result of each imputed data set will be combined using Rubin's rule {Rubin 1987}. Stratification factors and baseline values will be included in the imputation model as covariates.

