6.4.2. Analysis Methods for Secondary Efficacy Endpoints

Each secondary endpoint will be analyzed using a mixed-effect repeated measures (MMRM) model with treatment, randomization stratification factors, visit, treatment-by-visit interaction as fixed effects, subjects as a random effect, and the respective baseline value (ESSDAI or ESSPRI) as a covariate. The Kenward-Roger method will be used to estimate the degrees of freedom. Each of the four endpoints will be tested separately at the 2-sided 0.05 level. The unstructured (UN) variance-covariance matrix of repeated measures will be considered first. If a model does not converge, then ARH(1) structure will be applied.

For each secondary endpoint, adjusted means (LS means) and 95% confidence intervals (CIs) obtained from the model will be presented for Weeks 12 and Week 24 time points.

Missing data will be handled using the method described in [Table 3](#).

The inferential analyses of the secondary endpoints will be based on the treatment policy estimand (main analysis of each secondary endpoint). Sensitivity non-parametric analyses of the secondary endpoints will be performed on rank-transformed data utilizing ANCOVA models with treatment group and stratification factors as effects and the rank-transformed baseline value as a covariate.

In addition, secondary efficacy analyses will be repeated for the hypothetical estimand and composite estimand.

Descriptive statistics (n, mean, SD, median, Q1, Q3, minimum, and maximum) will be presented by visit and treatment group, overall and for the subgroups listed in [section 3.4](#).

Line plots for median (Q1, Q3) change from baseline, mean (+/- 95% CI) change from baseline, and adjusted mean (LS mean) change from baseline (+/- 95% CI) will be provided for ESSDAI total score, ESSPRI total score and its components.

In addition, the box plots for ESSDAI total score and ESSPRI total score and change from baseline will be presented by visit and treatment group.

A cumulative plot of change from baseline in ESSDAI total score and in ESSPRI total score at Week 12 and Week 24 will be presented by treatment group.

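### The imputation model for the main ESSDAI and ESSPRI analyses names neither treatment arm nor earlier visits; followed as listed, it shrinks the treatment effect

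*SAP*

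**What the plan says.** SAP section 6, Table 3, sets the main estimator for the continuous endpoints under the treatment-policy estimand: "The treatment difference will be estimated using a mixed effects model for repeated measures", followed by "Missing data will be imputed using multiple imputation". The hypothetical estimand has the same estimator. The composite estimand imputes from observed placebo data.

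SAP 6.1 describes the imputation for continuous variables: "Twenty imputed datasets will be generated based on linear regression models on observed values". It fixes the order of the steps: "These multiple imputed data sets are then analyzed by using the analysis method specified in Section 6.4 for complete data". The covariates it names are these: "Stratification factors and baseline values will be included in the imputation model as covariates". Treatment arm is not named, nor is any earlier post-baseline visit. Nothing says that the list is complete.

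SAP 6.4.2 specifies an MMRM with "treatment, randomization stratification factors, visit, treatment-by-visit interaction as fixed effects", subject as a random effect and the baseline score as covariate. On covariance it says "The unstructured (UN) variance-covariance matrix of repeated measures will be considered first", with ARH(1) as the fallback. On missing data it refers back to Table 3: "Missing data will be handled using the method described in". No MMRM on the observed data alone is planned, even as a sensitivity analysis. The rank-based ANCOVA in 6.4.2 addresses distribution, not missing data.

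**The concern.** An MMRM fitted to the observed data uses two pieces of information about a subject who leaves: the arm, through treatment-by-visit, and the subject's earlier scores, through the covariance matrix. Once every visit has been filled in, the model can no longer recover what the imputation ignored. ESSDAI is scheduled at Weeks 4, 8, 12 and 18 before Week 24, and ESSPRI also at Week 2, so there is information to lose.

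If arm is absent from the imputation model, an active and a placebo subject with the same baseline and stratum get imputed values with the same mean. That pulls the arms together. If earlier visits are absent, a subject who was doing badly is imputed as an average subject. That biases the contrast when such subjects leave one arm more than another. All four secondary endpoints are exposed, and two programmers could both comply with 6.1 and report different effects.

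**Working it through.** **Inputs.** From the SAP: impute first, 20 data sets, linear regression, strata and baseline named, then the 6.4.2 model. The plan has no figure of its own to reproduce: it gives no SD, visit correlation, effect or dropout rate for ESSDAI or ESSPRI, and its sample-size statement concerns the binary primary endpoint. Assumed here: SD 5, visit correlation 0.5-0.7 and a true effect of -2.0, with dropout as stated below. Completed data were analysed visit by visit with ANCOVA, standing in for the MMRM with unstructured covariance.

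**Step 1: arm omitted, dropout unrelated to outcome.** Let a share m be missing in each arm, with arm means A and P and a common imputed mean C. The completed-data difference is

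[(1-m)A + mC] - [(1-m)P + mC] = (1-m)(A-P).

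With A-P = -2.0 this gives -1.80, -1.60 and -1.40 at m = 10%, 20% and 30%, a loss of 10%, 20% and 30%. The simulation gave about 10%, 19% and 30%. With arm in the model nothing is lost in this setting.

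**Step 2: poor responders leave.** Baseline and Weeks 4, 8, 12, 18 and 24 were simulated with 200,000 subjects per arm. Dropout depended on the last observed change. Loss of the Week 24 effect by overall share missing at Week 24:

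| Imputation model | 10% missing | 20% missing | 30% missing |
|---|---|---|---|
| Baseline and strata, as listed | 11-14% | 22-26% | 32-37% |
| Earlier visits, no arm | about 6-8% | about 12-15% | about 18-22% |
| Baseline, strata and arm | 2-5% | 3-8% | 4-10% |
| Arm and all earlier visits | none | none | none |

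The first row corresponds to effects of -1.71 to -1.78, -1.48 to -1.56 and -1.25 to -1.35. The second corresponds to -1.85 to -1.88, -1.71 to -1.75 and -1.57 to -1.63; for example (2.0-1.88)/2.0 = 6%. The last row gave -1.98 to -2.01 at both Week 12 and Week 24. The Week 12 loss on the listed covariates was 6-8%, 13-17% and 19-24%.

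**Step 3: earlier visits omitted, arm included.** A separate simulation (60 replicates of 4,000 per arm) had dropout after Week 8 driven by a poor Week 8 change. Week 12 bias toward zero:

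| Dropout, placebo/active | Bias (points) | Share of 2.0 |
|---|---|---|
| 15%/15% | -0.01 to 0.01 | none |
| 20%/10% | 0.14-0.15 | about 7% |
| 30%/15% | 0.20-0.21 | about 10% |
| 30%/10% | 0.27-0.30 | about 14-15% |

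Adding Weeks 4 and 8 cut the bias to 0.02 or less. Equal dropout gives no bias because the selection cancels between arms. These losses exceed the third row of Step 2 because dropout is more unequal: in Step 2 the 30% case was, for example, 35%/25% placebo/active.

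**Step 4: trial size.** With 35 per arm, 20 imputations, Rubin's rules, correlation 0.6, a true effect of -3.0 and 39%/26% missing at Week 24 (placebo/active; 1,500 replicates):

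| Analysis | Mean effect | Power |
|---|---|---|
| Full data | -3.03 | 87% |
| Listed covariates | -1.85 | 27% |
| Listed covariates and arm | -2.79 | 62% |
| Arm and all earlier visits | -3.03 | 68% |

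**Limits.** Strata were given no prognostic effect. Neither retained off-treatment visits nor the early-termination rule was modelled.

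**The case against.** **The SAP does not say that only these covariates are used.** This stands. A reader might infer that arm and earlier visits are deliberately excluded; SAP 6.1 says that strata and baseline will be included and stops there. Its phrase about regression on observed values could describe sequential regression through earlier visits. But 6.1 does not say so, and that reading does not bring in the arm. Sequential imputation without arm still lost about 6-22% at Week 24.

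**Imputing before an MMRM is legitimate.** This also stands. A reader might infer that handling missing data twice is the flaw. The calculations contradict that: once arm and earlier visits are in the imputation model, the effect is recovered although imputation still comes first. Imputation also retains every subject with a baseline measurement, including those with no post-baseline visit, whom an MMRM on observed data drops.

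**The plan limits missingness.** Protocol 3.4 asks sites to keep subjects who stop dosing in the study. SAP 3.9 uses their data under treatment policy. SAP 3.8.2 assigns early-termination data to the next scheduled visit, with an unclearly worded exception. All of this would reduce the loss. It helps less under the hypothetical estimand if data after an intercurrent event are set to missing, as Table 3 states for the binary endpoint.

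**The earlier-visit part is small.** This is fair. Against standard errors of 0.976-1.186 at 35 per arm, a bias of 0.14-0.15 is about 0.12-0.15 standard errors (0.14/1.186 to 0.15/0.976), and these are secondary endpoints in a proof-of-concept trial. The same defence does not cover the omitted arm.

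**Conclusion.** The concern holds as an under-specified imputation model in the main estimator of all four secondary endpoints. Followed literally, the list attenuates the effect roughly in proportion to missingness because arm is absent, whatever the reason for dropout. Leaving out earlier visits adds a smaller bias, about 2-10% at Week 24 for 10-30% missing. That part needs unequal dropout between arms; poor responders leaving is not enough by itself. It ran toward no effect in the cases simulated because more subjects left placebo. By the same reasoning, it would flatter an active arm that lost more of its poor responders.

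The mechanism follows from the text and the arithmetic in Step 1. The size rests on the assumed SD, correlation, effect and dropout, none of which the documents give. A reader might carry these figures over to the binary primary endpoint; every calculation here concerns a continuous score, so they do not support that.

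**What to change.** In SAP 6.1, Table 3 and 6.4.2, for the treatment-policy and hypothetical estimands, choose one of two routes and state it:

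- Fit the 6.4.2 MMRM directly to the non-missing data, with no prior imputation. Arm and earlier visits then enter through treatment-by-visit and the covariance. The small cost is that subjects with no post-baseline visit drop out.
- Keep multiple imputation, but impute sequentially by visit with treatment arm, strata, baseline and all earlier visits in the model.

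Keep the placebo-based imputation for the composite estimand. Either route needs only a few sentences of SAP wording and no new data; the first also reduces programming. SAP section 1 says that the plan is finalized before the Week 24 analysis, so the change belongs before that point.

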3.9. Efficacy Estimands

Three efficacy estimands: a treatment-policy estimand, a hypothetical estimand and a composite estimand, are defined for the primary and secondary efficacy endpoints.

The **treatment-policy estimand** is the primary estimand for the primary and secondary efficacy endpoints.

1) Population: Subjects in the FAS

- 2) Variable: Primary and secondary endpoints
- 3) Intercurrent events: The occurrence of an intercurrent event is irrelevant. All observed values will be used regardless of occurrence of an intercurrent event

The **hypothetical estimand** is defined as following. This is the supportive estimand for the primary and secondary efficacy endpoints.

- 1) Population: Subjects in the Full Analysis Set (FAS).
- 2) Variable: Primary and secondary endpoints
- 3) Intercurrent events: The following intercurrent events are taken into account:
 - Subject takes prohibited medication
 - Subject changes the dose of the medication required to be stable per protocol
 - Subject discontinues from study treatment

The **composite estimand** is defined as following. This is the supportive estimand for the primary and secondary efficacy endpoints.

- 1) Population: Subjects in the Full Analysis Set (FAS).
- 2) Variable: Primary and secondary endpoints
- 3) Intercurrent events: The following intercurrent events are taken into account:
 - Subject takes prohibited medication
 - Subject changes the dose of the medication required to be stable per protocol
 - Subject discontinues from study treatment

The estimators associated with each of these estimands are described in [Table 3](#) of Section 6.

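### For ESSDAI and ESSPRI, SAP Table 3 gives no rule for data after an intercurrent event, and its composite estimator is placebo-based imputation rather than a composite strategy

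*SAP*

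**What the plan says.** SAP 3.9 defines three estimands for the primary and secondary endpoints. For treatment policy it gives a data rule: "All observed values will be used regardless of occurrence of an intercurrent event". For the hypothetical and the composite it lists the same three events (stopping study drug, taking a prohibited medicine, changing the dose of a background medicine meant to stay stable) and says, in the same words for both, only that they are taken into account. Of each it says "This is the supportive estimand for the primary and secondary efficacy endpoints". It sends the reader to Table 3 for the estimators.

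The binary half of Table 3 completes the definitions. Under hypothetical: "Data after the event are treated as missing". Under composite: "Data after the event are treated as no response".

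The continuous half lists the events again but carries no such sentence. Its treatment-policy and hypothetical estimator cells are identical: "The treatment difference will be estimated using a mixed effects model for repeated measures. Missing data will be imputed using multiple imputation". The composite cell differs only in its source of imputation: "Missing data will be imputed using multiple imputation based on observed data from the placebo group".

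SAP 6.4.2 states that "secondary efficacy analyses will be repeated for the hypothetical estimand and composite estimand" and refers back to Table 3 for missing data. SAP 6.1 describes one imputation for continuous variables, not split by estimand. SAP 6.6 records that the estimands were added in the SAP. Protocol 8.5.2, on secondary analyses, is blacked out in the public copy, so nothing can be inferred from it.

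**The concern.** What separates the three strategies is how data collected after an event are handled, and this trial sets out to collect such data. Protocol 3.1 and 3.4 keep subjects in follow-up after they stop study drug, where possible. Protocol 5.8 lets subjects who come off study drug because of a change in background treatment continue with visits. ESSDAI and ESSPRI values after an event will therefore exist at Weeks 12 and 24, and the continuous rows do not say whether they are used.

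Two consequences follow. A programmer who follows the table literally produces a hypothetical analysis that duplicates the main one, and a reader could take the agreement as support. And a result labelled composite would be reported from a method that does not make the event part of the outcome.

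**Working it through.** The plan gives no figure to reproduce here. The check is a comparison of the table cells, followed by simple algebra on what each estimator targets.

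**Cells side by side**

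| | Binary half | Continuous half |
|---|---|---|
| Hypothetical: post-event data | set to missing | not stated |
| Hypothetical: estimator | same wording as main | same wording as main |
| Composite: post-event data | counted as non-response | not stated |
| Composite: estimator | CMH, non-responder imputation | MMRM, placebo-based imputation |

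The binary hypothetical also shares its estimator with the main analysis ("Stratified CMH test with imputation of missing data using logistic regression"). It is distinct only through the data rule, which is the sentence the continuous half lacks. The binary composite rule cannot simply be carried over, since non-response has no defined value on a change score.

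**Size under assumptions**

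Effects are in units of the on-treatment effect (1.0), with mean placebo change set to 0. The documents give none of the following, so they are assumed:
- p, share of the active arm with an event: 10-30% (none in placebo)
- r, share of the effect retained in observed post-event values: 0 or 0.5
- m, share of event subjects whose values are truly missing: 0 or 0.5
- imputation within arm for the main and hypothetical analyses. SAP 6.1 lists the stratification factors and baseline as covariates, not treatment arm; if arm were left out, imputed values would pull towards no difference.

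Formulas:
- Main, and hypothetical read literally: [(1-p) + p(1-m)r] / [(1-p) + p(1-m)]
- Hypothetical with post-event values set to missing: 1
- Placebo-based, read literally: (1-p) + p(1-m)r
- Placebo-based with post-event values set to missing: 1-p

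Example, p = 0.20, r = 0.5, m = 0.5: main = (0.80 + 0.05)/(0.80 + 0.10) = 0.944; placebo-based, literal = 0.80 + 0.05 = 0.85; placebo-based with the rule = 0.80.

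Six of the 12 combinations, including both extremes of the main column:

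| p | r | m | Main = hypothetical, literal | Hypothetical with rule | Placebo-based, literal | Placebo-based with rule |
|---|---|---|---|---|---|---|
| 0.10 | 0.5 | 0.5 | 0.974 | 1.0 | 0.925 | 0.90 |
| 0.20 | 0 | 0 | 0.80 | 1.0 | 0.80 | 0.80 |
| 0.20 | 0.5 | 0 | 0.90 | 1.0 | 0.90 | 0.80 |
| 0.20 | 0.5 | 0.5 | 0.944 | 1.0 | 0.85 | 0.80 |
| 0.30 | 0 | 0 | 0.70 | 1.0 | 0.70 | 0.70 |
| 0.30 | 0.5 | 0 | 0.85 | 1.0 | 0.85 | 0.70 |

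Read literally, main and hypothetical agree in all 12 combinations, apart from random variation between imputations. With the rule, the gap runs from 1 - 0.974 = 0.026 to 1 - 0.70 = 0.30. Read literally with nothing truly missing (m = 0), the placebo-based analysis also equals the main one.

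**Placebo-based imputation against a scored event**

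Let an event score u, with shares pa (active) and pp (placebo). A composite then targets (1-pa) + pa·u - pp·u. Placebo-based imputation with post-event values dropped targets 1-pa. The difference is u(pa - pp). With u = -1 (assumed):
- pa = 0.20, pp = 0.10: composite 0.70, placebo-based 0.80
- pa = pp = 0.20: both 0.80
- pa = 0.10, pp = 0.20: composite 1.0, placebo-based 0.90

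The two targets coincide when event shares are equal or when the score happens to equal the mean placebo change. Otherwise they differ, in a direction set by which arm has more events.

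**The case against.** A reader might infer that neither supportive estimand is estimated and that the hypothetical result equals the main result by construction. The documents do not support that. SAP 3.9 reserves the use of all observed values for treatment policy and contrasts it with events that are taken into account. Keeping post-event values in every analysis would empty that contrast. A shared estimator is no defect in itself, as the binary half shows. The continuous half also drops the population row, so it reads as an abbreviated continuation in which the same rule was probably intended. For the hypothetical, what stands is under-specification.

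A reader might also infer that the SAP describes the ESSDAI and ESSPRI composite as counting events as failures. It does not: non-response language appears only in the binary half, and the continuous cell openly states placebo-based imputation. The fault is the mismatch between label and method. Nor does the SAP call the hypothetical and composite repeats of the secondary endpoints sensitivity analyses; in 6.4.2 that term belongs to the rank-based ANCOVA.

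Finally, this is a proof-of-concept study without multiplicity adjustment (SAP 3.5), and these are supportive repeats. That limits the weight of the point but leaves both gaps open.

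**Conclusion.** The point holds in two parts. First, the continuous half of Table 3 omits the post-event data rule. Followed literally, the hypothetical analysis duplicates the treatment-policy analysis; with the binary rule carried over, it would differ by 0.03 to 0.30 of the on-treatment effect. That range rests on the assumed event shares, retained effect and within-arm imputation above, not on figures from the documents.

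Second, and regardless of how the first gap is read, the estimator labelled composite is a reference-based missing-data analysis. No section gives an ESSDAI or ESSPRI value or rank to the event itself, so a composite estimand is not estimated for these endpoints.

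The reach is limited to supportive analyses of secondary endpoints. The primary endpoint has its own explicit rules in the binary half, and the main secondary analysis is the treatment-policy one, so neither is touched. The correction is cheap and should be made.

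**What to change.** Amend the continuous rows of Table 3 before the Week 24 unblinding:

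1. Hypothetical: state that values after an event are set to missing before imputation, as in the binary row.
2. Placebo-based analysis: state that post-event values are set to missing here too, and relabel it as reference-based (placebo-based) imputation so that it is not reported as a composite result.
3. If a composite estimand is still wanted, prespecify one unfavourable value or rank to apply after an event. The choice of score, and whether to analyse it by the planned MMRM or by ranks, is the sponsor's.

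The SAP 3.9 text for the hypothetical and composite estimands should be made to match. The cost is wording and a small amount of programming. The placebo-based result may look somewhat less favourable: in the scenarios above it falls by p(1-m)r, from 0 (where no effect is retained) to 0.30 × 1 × 0.5 = 0.15 of the on-treatment effect.
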